## **9 HUMAN SUBJECTS PROTECTIONS**

### **9.1 RATIONALE FOR SUBJECT SELECTION**

Subjects from all racial/ethnic groups are eligible for this study if they meet the eligibility criteria. Efforts will be made to extend accrual to a representative population.

### **9.2 PARTICIPATION OF CHILDREN**

Children are excluded from this study because endoscopic screening for CDH1 mutation carriers is not recommended in children.

### **9.3 PARTICIPATION OF SUBJECTS UNABLE TO GIVE CONSENT**

Adults unable to give consent are excluded from enrolling in the protocol. However, re-consent may be necessary and there is a possibility, though unlikely, that subjects could become decisionally impaired. For this reason and because there is a prospect of direct benefit from research participation (Section 9.5), all subjects will be offered the opportunity to fill in their wishes for research and care, and assign a substitute decision maker on the “NIH Advance Directive for Health Care and Medical Research Participation” form so that another person can make decisions about their medical care in the event that they become incapacitated or cognitively impaired during the course of the study. Note: The PI or AI will contact the NIH Ability to Consent Assessment Team (ACAT) for evaluation as needed for the following: an independent assessment of whether an individual has the capacity to provide consent; assistance in identifying and assessing an appropriate surrogate when indicated; and/or an assessment of the capacity to appoint a surrogate. For those subjects that become incapacitated and do not have pre-determined substitute decision maker, the procedures described in NIH HRPP SOP 14E for appointing a surrogate decision maker for adult subjects who are (a) decisionally impaired, and (b) who do not have a legal guardian or durable power of attorney, will be followed.

### **9.4 PARTICIPATION OF PREGNANT WOMEN**

Pregnant women with CDH1 germline mutations are at the same risk for developing gastric cancer than non-pregnant women. For this reason and because there is a prospect of direct benefit from research participation (Section 9.5.3) pregnant women will be included in this study. In addition, some women who are pregnant may require endoscopic screening depending on the timing of diagnosis or the presence of gastrointestinal symptoms. If an endoscopy is indicated, and the patient wishes to be enrolled, there is no reason that they should be excluded from the protocol. Women undergo invasive abdominal and thoracic surgery if needed during pregnancy. Pregnant women will not receive the intravenous contrast agent, fluorescein, if they are enrolled.

### **9.5 EVALUATION OF BENEFITS AND RISKS/DISCOMFORTS**

These evaluations apply to all participants. All care will be taken to minimize side effects, but they can be unpredictable in nature and severity. This study may involve risks to patients, which are currently unforeseeable.

### 9.5.1 Risks for All Participants Including Subjects Unable to Consent

#### *Risks of Upper Endoscopy*

The risks of upper endoscopy include, but are not limited to, temporary throat soreness, gastrointestinal bleeding, and rarely gastrointestinal perforation.

#### *Risks of Fluorescein Intravenous Administration*

The risks of intravenous administration of the contrast agent fluorescein are: nausea, vomiting, dizziness, headache, and low blood pressure.

#### *Risks of General Anesthesia*

The risks of general anesthesia include, but are not limited to, temporary confusion and memory loss, dizziness, difficulty passing urine, bruising or soreness from the IV drip, nausea and vomiting, shivering and feeling cold, sore throat, heart attack, pneumonia and stroke.

#### *Risk of Biopsies*

All care will be taken to minimize risks that may be incurred by tumor sampling. Biopsies will be taken during endoscopy. All procedure-related risks (such as bleeding, infection and visceral injury) will be explained fully during informed consent.

### 9.5.2 Benefits for All Participants Including Subjects Unable to Consent

The benefit is detection of gastric cancer at its earliest stage so that it is potentially curable.

### 9.5.3 Risk/Benefit Analysis for Pregnant Women

The benefit is detection of gastric cancer at its earliest stage so that it is potentially curable. We will be following the anesthesia guidelines for pregnant women, i.e., waiting until the second trimester. All described risks described in Section 9.5.1 apply for pregnant women and there are also additional risks, including fetal loss, premature labor, and delivery.

## **9.6 CONSENT PROCESS AND DOCUMENTATION**

The investigational nature and research objectives of this trial, the procedures and treatments involved and their attendant risks and discomforts and benefits, and potential alternative therapies will be carefully explained to the patient, and a signed informed consent document will be obtained by a study investigator prior to entry onto the study.

The PI or associate investigator will meet with the patient to discuss the protocol treatment and alternative options in detail. It will be stated clearly that participation in the research study is voluntary and that participants can withdraw from the study without losing benefits they would otherwise be entitled to. The patient will be encouraged to ask questions, and additional meetings to discuss the treatment options will be arranged as necessary.

### 9.6.1 Telephone Consent

The informed consent document will be sent to the subject. An explanation of the study will be provided over the telephone after the subject has had the opportunity to read the consent form. The subject will sign and date the informed consent. The original informed consent document

will be sent back to the consenting investigator who will sign and date the consent form with the date the consent was obtained via telephone.

A fully executed copy will be returned via mail for the subject's records.

The informed consent process will be documented in the medical record.

## **10 DEVICE INFORMATION**

There will be no IDE obtained for the use of Cellvizio® 100 Series systems with Confocal Miniprobos™ and Olympus GIF 180 endoscope in this study.

The devices used on this study, the Cellvizio® 100 Series systems with Confocal Miniprobos™ and Olympus GIF 180 endoscope, meet the requirements for exemption under 21 CFR 812.2.C.2, "A device, other than a transitional device, introduced into commercial distribution on or after May 28, 1976, that FDA has determined to be substantially equivalent to a device in commercial distribution immediately before May 28, 1976, and that is used or investigated in accordance with the indications in the labeling FDA reviewed under subpart E of part 807 in determining substantial equivalence."

### **10.1 SOURCE**

Cellvizio® 100 Series systems with Confocal Miniprobos™ will be purchased from Mauna Kea Technologies and Olympus GIF 180 endoscope will be purchased from Global Endoscopy Solutions.

## 12 APPENDICES

### 12.1 APPENDIX A: CLINICAL CRITERIA FOR GENETIC TESTING DUE TO A HISTORY SUGGESTIVE OF HEREDITARY DIFFUSE GASTRIC CANCER (HDGC) SYNDROME

Criteria	Definition
1	Family with 2 or more cases of GC regardless of age, with at least one confirmed DGC
2	One case of DGC at age < 40 years
3	Personal or family history of both DGC and LBC, with one diagnosed at age < 50 years
Expanded criteria	
	Bilateral LBC or family history of 2 or more cases of LBC at age < 50 years
	A personal or family history of cleft lip/palate in a patient with DGC
	In situ signet ring cells and/or pagetoid spread of signet ring cells on stomach biopsy
GC, gastric cancer; DGC, diffuse gastric cancer; LBC, lobular breast cancer

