## **PRÉCIS**

### **Background:**

- Hereditary Diffuse Gastric Cancer (HDGC) syndrome is caused by a germline mutation in the CDH1 gene. Carriers of this mutation have a 56-70% lifetime risk of developing gastric adenocarcinoma. Current international guidelines recommend endoscopic screening of CDH1 mutation carriers that consists of systematic biopsies of an otherwise normal appearing stomach. However, this approach lacks sufficient sensitivity for detecting intramucosal foci of signet ring cells (SRC), which are pathognomonic of HDGC syndrome. The goal of the current study is to utilize confocal endoscopic microscopy (CEM) for screening the gastric mucosa in this high-risk population.

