## **2 ELIGIBILITY ASSESSMENT AND ENROLLMENT**

### **2.1 ELIGIBILITY CRITERIA**

#### **2.1.1 Inclusion Criteria**

- Patients with CDH1 germline mutation known to be pathogenic or likely pathogenic, which may also be classified as “significant” or “likely significant” (patients with variants of “uncertain significance” are excluded).

**or**

- Patients with CTNNA1 and PALB2 germline mutations suspected to be, or reported to be, associated with HDGC.

**or**

- In the absence of a germline CDH1 mutation, patients must meet clinical criteria for genetic testing due to a history suggestive of Hereditary Diffuse Gastric Cancer (HDGC) syndrome ([Appendix A](#)).
- Age  $\geq$ 18 years.
- Physiologically able to undergo upper endoscopy.
- Ability to understand and the willingness to sign a written informed consent document.

- Pregnant women are eligible during second trimester of pregnancy if clinically indicated for evaluation of cancer.

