### 2.1.2 Exclusion Criteria

- Current use of therapeutic anticoagulation medication.
- Known bleeding disorder or thrombocytopenia.
- Unstable angina or recent (within 3 months) myocardial infarction.
- Any clinical contraindication to general anesthesia.

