### 2.3.1 Intervention Assignment Procedures (For Registration Purposes Only):

#### Cohorts

Number	Name	Description
1	Cohort 1	Subjects with CTNNA1, PalB2 or known to be pathogenic or likely pathogenic CDH1 germline mutations, or those who test negative for these mutations, but meet clinical criteria for HDGC.

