## **8.2 SAMPLE SIZE DETERMINATION**

Subjects who are carriers of a CDH1 mutation and participate in this trial will undergo an EGD and detailed gastric mapping along with confocal laser microscopy. Based on the historical data from NIH, 17 patients who were CDH1 mutation carriers and who underwent an EGD and detailed gastric mapping resulted in 4 with signet ring foci detected. All 4 of these patients eventually were found to have gastric cancer after undergoing a prophylactic gastrectomy. An additional 18 patients who had prophylactic gastrectomy out of 39 who had conventional random biopsies yielded 8 patients with gastric cancer.

Based on the current historical rate of 4/17 (23.5%) of mapped patients who had signet ring foci detected, it would be desirable to see if use of confocal laser microscopy could increase this detection rate substantially. With 36 patients undergoing EGD with detailed gastric mapping and confocal laser microscopy, there would be 89% power to rule out a 24% rate of signet ring detection in favor of a rate of detection consistent with 45%, with a one-sided 0.10 significance level exact binomial test. In practice, if 36 patients would undergo the procedure described and if 13/36 (36.1%) would have signet ring foci identified, then the lower one-sided 90% confidence bound on 13/36 is 25.3%, which would demonstrate statistically greater detection in the subjects tested compared to the historical fraction of 4/17 (23.5%). In addition, the upper one-sided 90% confidence bound on 13/36 is 48.2%, which demonstrates that 13/36 could be shown to be consistent with as great as a 45% detection rate.

It is expected that 18-20 patients may enroll on this study per year. Thus, to enroll 36 evaluable patients, approximately 24 months is the expected accrual period. To allow for a small number of inevaluable patients, the accrual ceiling will be set at 40 patients.

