## **8.3 POPULATIONS FOR ANALYSES**

All patients who undergo an EGD and gastric mapping along with confocal endoscopic microscopy.

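### Patients with signet ring cells already proven on an earlier stomach biopsy can enter and are counted in the fraction compared with 24%, so case mix alone can move the primary result

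*Combined protocol and SAP*

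**What the plan says.** The Précis gives the aim as to "utilize confocal endoscopic microscopy (CEM) for screening the gastric mucosa in this high-risk population".

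Entry has three routes in section 2.1.1:

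- The first is "Patients with CDH1 germline mutation known to be pathogenic or likely pathogenic", with no condition on earlier biopsy results.
- The second is a CTNNA1 or PALB2 mutation, also without such a condition.
- The third applies when no CDH1 mutation is present: "patients must meet clinical criteria for genetic testing due to a history suggestive of Hereditary Diffuse Gastric Cancer (HDGC) syndrome". Those criteria are in Appendix A, and one of its expanded criteria is in situ "signet ring cells and/or pagetoid spread of signet ring cells on stomach biopsy".

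Section 2.1.2 has four exclusions: anticoagulation, bleeding disorder or thrombocytopenia, recent cardiac events, and "Any clinical contraindication to general anesthesia". None concerns an earlier SRC finding. Section 2.3.1 places all entrants in one cohort, including "or those who test negative for these mutations, but meet clinical criteria for HDGC".

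Section 8.3 defines the analysis population as "All patients who undergo an EGD and gastric mapping along with confocal endoscopic microscopy". Section 8.4.1 reports the fraction of them with SRC foci identified. It does not separate new foci from known ones, or CEM findings from mapping findings. Section 8.2 takes its benchmark from 4 of 17 historical mapped patients, described as CDH1 carriers, and states that with 36 patients "there would be 89% power to rule out a 24% rate of signet ring detection" in favour of 45%. No analysis by earlier SRC status is planned.

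**The concern.** The trial is meant to show how often occult foci are found on screening. A patient who qualifies because a biopsy has already shown SRC is not being screened in that sense. The study procedure can only find again what is known to be there, and the endoscopist may know the site.

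The design has one arm and a fixed historical comparator, so no concurrent control absorbs a change in case mix. If known-SRC patients yield SRC at the study endoscopy more often than 24%, the fraction rises whether or not CEM contributes. Each patient also has 30 mapping biopsies (section 3.2.2), which can find SRC again without CEM. A result of 13/36 could then be read as evidence for CEM when part of it reflects who was enrolled.

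Restricting the analysis to CDH1 carriers, as the primary objective is worded, would close the Appendix A route. It would not remove a carrier with an earlier positive biopsy.

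**Working it through.** **Inputs from section 8.2:** n = 36, null rate 24%, alternative 45%, one-sided 0.10 exact binomial test, illustrative success at 13/36.

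**Step 1, reproduce the design.** With X ~ Bin(36, p):

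- P(X ≥ 13) at p = 0.45 is 0.893, which agrees with the stated 89%.
- P(X ≥ 13) at p = 0.24 is 0.070.
- P(X ≥ 12) at p = 0.24 is 0.133, above 0.10, so 13 is the right cut-off.

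**Step 2, add known-SRC patients.** Let k of the 36 have earlier biopsy-proven SRC and be re-detected with probability q. Let the other 36 − k stay at the 24% null, so that CEM adds nothing for them. Then X = Bin(k, q) + Bin(36 − k, 0.24). P(X ≥ 13) follows from the exact convolution of the two. The documents give neither k nor q, so a range is shown.

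| q | k = 2 | k = 4 | k = 6 |
|---|---|---|---|
| 24% | 7.0% | 7.0% | 7.0% |
| 26% | 7.3% | 7.5% | 7.7% |
| 45% | 9.5% | 12.5% | 16.2% |
| 50% | 10.1% | 14.1% | 19.0% |
| 80% | 14.2% | 25.7% | 41.3% |
| 100% | 17.2% | 35.5% | 60.4% |

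For k = 4 and q = 80%, the expected fraction is (4 × 0.80 + 32 × 0.24)/36 = 10.88/36 = 30.2%, against the null of 24%.

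**Step 3, what the documents suggest about q.** Section 1.2 says foci occupy less than 2% of the mucosa. If the 30 biopsies were independent random samples (an assumption), the chance of at least one hit is 1 − (1 − f)^30 for involvement f. This gives 45% at f = 2%, 26% at 1% and 14% at 0.5%. These values concern occult disease in general. Patients already biopsy-positive may have more disease or a known site, so the values are not upper limits for them. At q = 14%, four such patients lower P(X ≥ 13) to 5.0%.

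**Step 4, an opposing pull.** Suppose 4 known-SRC patients are re-detected at 75%, 10 other mutation-negative patients have an assumed 10% rate, and the remaining 22 are at 24%. The same convolution gives P(X ≥ 13) = 9.1%, below the nominal 10%. With the 4 known-SRC patients and the other 32 at 24%, it would be 23.5%.

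**The case against.** The strongest reply is that the effect may be small or absent. Section 1.2 says that patients with SRC on biopsy are advised to have a total gastrectomy, and section 8.2 reports that all 4 historical mapping-positive patients had one. Few may therefore enrol for a further endoscopy. The figures on focus size point to modest re-detection, and at 26% the inflation is negligible. Mutation-negative patients may pull the fraction down. The earlier biopsy history of the 17 historical patients is not stated, so the benchmark may already contain a similar mix. All of this stands, and it limits the size that can be claimed. It does not close the route: advice to have surgery is not an exclusion criterion, and an offset that is neither measured nor controlled does not make the comparison sound.

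A reader might infer three stronger things that the documents do not support.

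- **That an earlier positive biopsy counts as a detection, or that the outcome is known in advance.** Section 8.4.1 requires SRC to be identified in patients undergoing the study procedure, so there is inflation only if re-detection exceeds 24%.
- **That the 17 − 4 = 13 mapping-negative historical patients are under surveillance at this centre and will re-enter.** Section 1.2 gives only a general recommendation of annual surveillance for those who decline gastrectomy. Nothing bars these patients from enrolling, but nothing says they will.
- **That those patients should be removed.** If all 13 enrolled, 40 − 13 = 27 would remain. The exact rule would be 10/27, with power 0.85 before any other losses. A with-and-without analysis answers the question at less cost.

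**Conclusion.** The point holds as a gap in the plan's rules. Patients with known SRC can enter, by a named criterion or because no criterion stops them, and they are included in the fraction compared with a fixed 24%. The design figures themselves are correct (power 89.3%, actual alpha 7.0%).

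With four such patients and no CEM effect, the chance of meeting the rule runs from 7.5% at 26% re-detection to 36% at 100%. It passes the nominal 10% at 45% re-detection (12.5%). These figures rest on an assumed number of patients and an assumed rate, with everyone else at 24%. The net direction in the enrolled population cannot be settled from the documents. The point therefore supports a pre-specified safeguard, and does not support a claim that the trial will succeed falsely. Severity: should-fix.

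**What to change.** 1. **Section 2.2:** record the date and result of every earlier gastric biopsy, as part of the medical history already taken.
2. **Section 8.3:** state, before results are seen, that the primary comparison with 24% uses patients with no biopsy-proven SRC before the study endoscopy. Recompute the exact cut-off for the number achieved. With 34 patients it is 12/34 (alpha 0.093, power 0.91).
3. **Section 8.4:** report known-SRC patients separately for the detected fraction. Do the same in the false negative analysis, since knowledge of an earlier positive site could flatter CEM there too.
4. **Historical mapped patients:** keep any who re-enrol in the primary set, and show the primary result with and without them as a sensitivity analysis.

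The cost is one screening field and a few sentences, and eligibility does not change. A few patients leave the primary set. The 40 − 36 = 4 places above the target are already meant for inevaluable patients, so they cannot be relied on to replace them, and power may fall slightly. Because the exact test moves in steps, 32 patients would need 12/32 (alpha 0.062, power 0.85).
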